Once such regions are identified, the group peaks of activation in these regions will be used as 4-mm seed regions for functional connectivity analysis ([name], 2003) using AFNI software to determine the *trait characteristics* of voice-controlling networks in SD and SD/VT. For this, we will use psychophysiological interactions (PPI) analysis, which refers to significant changes in the contribution of one brain region's activity to that in another region due to changes in the experimental or psychological context (Friston et al., 1997). Time series during task production and silent fixation will be extracted from each seed region in each subject and multiplied by the task vector with the follow-up regression with the time series from the entire brain. The results of regression analysis will indicate the changes in interaction of the seed region with the entire brain relative to the examined condition (e.g., speech vs. silent fixation). A significant change in interaction will mean that the functional connectivity between the seed region and a given region in the brain is significantly different when the subjects perform one task compared with another. The subject-specific functional connectivity maps will be submitted to group analyses to identify differences within and between the groups at a corrected $p \leq 0.025$ to account for multiple comparisons. To further correct for multiple comparisons across the voxels in the whole brain at a group $p \leq 0.025$, we will esti-

mate the voxelwise probability of a false positive detection using Monte Carlo simulation with the individual voxel probability threshold of $p \leq 0.005$ and data-dependent minimum cluster size threshold.

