Following the initial (baseline) fMRI session, patients will receive an individualized tolerable and efficacious single dose of sodium oxybate, given orally in the office. Patients' symptoms will be evaluated and videotaped one hour after receiving this dose with the immediately followed-up second fMRI session, during which the patients will be asked to produce the same tasks performed during the pre-treatment fMRI study. Patients' post-treatment scans will be compared to their pre-treatment scans to identify differences in brain activation abnormalities due to the effects of sodium oxybate treatment. Voice and speech production during both scanning sessions will be digitally recorded for acoustical analysis and correlations with the central effects of the treatment.

Data analysis. Using AFNI software, fMRI data analysis will include initial pre-processing followed by analysis of the task-related responses using multiple linear regression with a single regressor for each task convolved with a canonical hemodynamic response function, as described above in *1.3.1 Study of Specific Aim #1*. For group analysis, a two-way ANOVA will be conducted with subject as a random factor and task as fixed factor (corrected $p \leq 0.025$). Conjunction analysis at a cluster significance threshold of $p < 0.005$ will determine common and distinct regions of activation within the patient group during task production in the pre- and post-treatment fMRI sessions. Finally, pre- and post-treatment neuroimaging findings will be correlated with the behavioral data derived from acoustical analysis of voice and speech recordings.

Additionally, to determine the extent of sodium oxybate effects on speech network dynamics, we will re-examine functional and effective network connectivity using the same PPI and DCM procedures as described in the *Study 1.3.1*.

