Study population and Sample size. To our knowledge the central effects of sodium oxybate has not been reported. Therefore, to estimate the number of patients to be included in this study, we reviewed our pilot fMRI study in SD and SD/VT patients. Compared to baseline, we found an average of 49% reduction of overly increased brain activation after treatment with sodium oxybate. Power analysis determined a sample size of 22 patients in each group to have 80% power at 0.025 to detect changes in brain activation when comparing before and after treatment conditions. We propose to recruit 25 ethanol-responsive SD and SD/VT subjects per group to account for the subjects' dropout possibilities and to increase statistical power.

2.3.2 Study #2: Evaluation of combined central effects of sodium oxybate and botulinum toxin treatments in patients with SD and SD/VT using fMRI during symptomatic speech production. In this study, we will use the same fMRI design as used in the Similar to *Studies 1.3.1* and *2.3.1* to examine the combined effects of sodium oxybate and botulinum toxin on brain activation changes due to the treatment.

We estimate that about 40% of all recruited patients (mostly with ADSD) will report some benefits from botulinum toxin injections. These patients will be enrolled in this study and will undergo the third scanning session after receiving their botulinum toxin treatment. They will be asked to take their individualized dose of sodium oxybate T.I.D. after the completion of the *Study 2.3.1* and until the end of this study. We predict that about 60% of SD (typically ABSD) and SD/VT patients recruited to the *Study 2.3.1* will report limited, if any, benefits from botulinum toxin treatment. These patients will, therefore, be replaced with newly recruited patients, whose symptoms do response to both alcohol intake and botulinum toxin treatment. Thus, at the time of this study, all patients will be treated with both sodium oxybate and botulinum toxin injections. The decision of whether sodium oxybate should be continued after the completion of all studies in this proposal will be made by the patient and his/her referring physician.

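### Study 2.3.1 sorts regions by a conjunction of the pre- and post-treatment maps, and no stated activation analysis tests the pre-to-post difference

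*Combined protocol and SAP*

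**What the plan says.** Section 2.3.1 of Specific Aim #2 states the purpose of the two scans: "Patients' post-treatment scans will be compared to their pre-treatment scans to identify differences in brain activation abnormalities due to the effects of sodium oxybate treatment". Its sample-size paragraph is built on the same purpose, giving a "sample size of 22 patients in each group to have 80% power at 0.025 to detect changes in brain activation" between the before and after conditions.

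The Data analysis paragraph of 2.3.1 then names these steps for activation:

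- First-level regression for each task.
- A two-way group ANOVA with subject random and task fixed, at a corrected 0.025. Session is not a factor.
- "Conjunction analysis at a cluster significance threshold of" p < 0.005, which "will determine common and distinct regions of activation within the patient group during task production in the pre- and post-treatment fMRI sessions".
- Correlation of the pre- and post-treatment imaging findings with the acoustic measures.

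A further paragraph re-runs the connectivity analyses (PPI and DCM). Section 2.3.2, the combined-treatment study, adopts the 2.3.1 pipeline unchanged.

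The figure 0.005 also appears in section 1.3.1, where it is the voxel-level cutoff ("using Monte Carlo simulation with the individual voxel probability threshold of" 0.005) and is paired with a corrected level of 0.025.

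**The concern.** A conjunction shows where both session maps pass a threshold. If it is also used to pick out *distinct* regions, the natural reading is that these pass in one session and fail in the other. That sets a significant result beside a non-significant one. It does not estimate or test the difference between sessions, and two equally active sessions will often fall on opposite sides of a cutoff by chance.

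Aim 2 exists to find the brain activation that sodium oxybate modulates. If readers take the one-session-only regions as the answer, some unaffected regions can be presented as drug effects. By symmetry about half of such errors are pre-only, the pattern that looks like attenuation. A region whose activation falls but stays above threshold is simply active in both maps, and the conjunction says nothing about its fall.

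**Working it through.** **Is a test of change written anywhere?** Each candidate, taken in turn:

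| Text | What it supplies |
|---|---|
| 2.3.1, comparison of post- with pre-treatment scans | An aim; no contrast or test named |
| 2.3.1, two-way ANOVA | Subject and task only; no session term |
| 2.3.1, conjunction | Where maps pass a threshold; no difference tested |
| 2.3.1, PPI and DCM | Connectivity, not activation |
| 2.3.1, correlation with acoustic data | Association with behaviour; does not classify regions as changed |
| 1.3.1, subtraction within the three-way ANOVA | Written for Aim 1 group contrasts; not carried into 2.3.1 |
| 2.2.2, paired *t*-test in the pilot | Applied to a whole-brain count of significant voxels; not carried into 2.3.1 |

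None is a specified test of the pre-to-post difference in activation.

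**How often would an unchanged location pass in exactly one session?** The plan gives no figure to reproduce.

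*From the documents:* cutoff p < 0.005, sidedness not stated.

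*Assumed:* two-sided test, so the critical value is 2.807; normal statistics; one test, no cluster correction; the same true activation in both sessions; per-session power *p*; correlation *r* between the two session statistics.

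*Formula:* P(exactly one) = 2 × (*p* − P(both)), where P(both) is the bivariate normal probability that both statistics exceed the cutoff.

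*Example at p = 0.80:*

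- *r* = 0: P(both) = 0.80 × 0.80 = 0.64, so 2 × (0.80 − 0.64) = 0.32.
- *r* = 0.8: P(both) = 0.729, so 2 × (0.80 − 0.729) = 0.142.

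| Per-session power | *r* = 0 | *r* = 0.6 | *r* = 0.8 |
|---|---|---|---|
| 50% | 50% | 30% | 20% |
| 80% | 32% | 20% | 14% |
| 95% | 10% | 7% | 5% |
| 99% | 2% | 2% | 1% |

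A direct paired test at the same two-sided 0.005 is wrong 0.5% of the time in every cell, by construction.

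**Check with *t* statistics at the planned size.** A simulation (20,000 replicates, n = 22, same cutoff) gave 50%, 32% and 10% at correlation 0 for power of 50%, 80% and 95%, and 22%, 15% and 5% at correlation 0.8. The paired test gave between 0.4% and 0.6%. Results at n = 25 were nearly the same.

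**Partial attenuation.** This needs no arithmetic. If activation falls but both sessions still exceed the cutoff, the location is in the conjunction, exactly as it would be had nothing changed. The rule returns the same label for both cases.

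**The case against.** The strongest reply is that a paired comparison is plainly intended. Section 2.3.1 says the scans will be compared, the sample size is for detecting change, and the pilot in 2.2.2 used a paired *t*-test. On that view the conjunction is a descriptive extra. The intent is plausible, and it is why the consequence is that regions *can* be mislabelled. It does not fill the gap, because no contrast is written and the model as stated has no term to carry one.

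Several stronger readings are tempting, and the documents do not support them:

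- *Unaffected regions will be reported as drug-modulated.* Section 2.3.1 speaks of regions of activation. It neither defines *distinct* nor equates it with modulated.
- *The rule errs in both directions because changed regions are called common.* Nothing says that *common* means unchanged. A region active in both sessions is correctly so described. What stands is that the conjunction cannot reveal a partial fall.
- *The planned 49% effect gives the rate of missed changes.* According to 2.2.2, the 49% is a drop in the total number of significantly active voxels. It is not a fall in signal within a region, so it cannot be used to scale a regional statistic.
- *A session term would not help while the conjunction remains.* Once change is judged on a tested contrast, the conjunction is harmless as description.
- *The 0.005 is a misprint for the voxel threshold.* It may be loose wording for that, or a stricter cluster level. The text does not settle which.

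It is also fair that the rates fall to 1-2% where activation is very strong, and that they ignore cluster correction.

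**Conclusion.** The plan is wrong as written on this point. Study 2.3.1 aims to detect a change in activation, states no test of it, and uses a conjunction to separate common from distinct regions. Study 2.3.2 inherits the gap.

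The size is conditional. For an unchanged location, passing in one session only has a chance of roughly 1% to 50% over per-session power of 99% down to 50% and correlation of 0.8 down to 0, against 0.5% for a paired test at the same level. The documents give neither input, so the actual rate is unknown. The figures are for a single test, not for clusters. That significance in one session alone does not test change holds whatever those values are.

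**What to change.** Amend the Data analysis paragraph of 2.3.1 as follows:

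1. Add session (pre/post) as a within-subject factor, or specify a voxelwise paired post-minus-pre contrast, at the corrected p ≤ 0.025 already used in the plan.
2. Call a region changed or drug-modulated only when that contrast passes.
3. Keep the conjunction solely to describe regions active in both sessions.
4. State whether p < 0.005 is the voxel threshold, as in 1.3.1, or a cluster-level threshold, and reconcile the sections.
5. Apply the same rule in 2.3.2, naming which pair of sessions each contrast compares.

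The cost is analysis-plan wording; no new data are needed. Fewer regions may be reported as modulated. The paired test can also have low power where activation is weak. As an illustration on assumed values only (pre-dose standardised mean 1.0, regional signal falling by 49%, correlation 0.5, n = 22, two-sided 0.005), simulation gave 23% power, rising to 69% at correlation 0.8. The change makes the claim valid but does not guarantee detection.

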II. Sodium oxybate modulates abnormally increased activation in SD and SD/VT patients. Using a sparse-sampling BOLD fMRI design and symptomatic speech production, we examine the effects of sodium oxybate on brain activation abnormalities in 3 SD and SD/VT patients to evaluate the mechanisms of central action of this novel pharmacological agent. Compared to healthy controls, before treatment, all patients exhibited typically increased brain activation during symptomatic speech production ($p \leq 0.05$, corrected) (Fig. 3-I) similar to abnormalities described before (Haslinger et al., 2005; Ali et al., 2006; [name] and Ludlow, 2010) and in our 1.2.2 *Preliminary Studies* above. After treatment, patients' brain activation was significantly attenuated and followed a nearly normal pattern present during normal speech production, with only few regions remaining hyperactive ($p \leq 0.05$, corrected) (Fig. 3-II). A two-tailed paired *t*-test calculation using the measure of the total number of significantly active brain voxels before and after treatment in patients showed that the drug-induced attenuation of abnormal functional activation was in average 49% ($p = 0.017$) (Fig. 3-III). Specifically, sodium oxybate treatment significantly decreased and normalized abnormally elevated brain activity in the prefrontal, premotor and auditory cortices as well as in the basal ganglia, thalamus, and cerebellum. In 1.2.2 *Preliminary Studies* presented above, we found these regions to have a greater extent of abnormal activation in SD/VT patients compared to SD patients.

[figure not shown]

Figure 3 depicts differences in brain activation in SD and SD/VT compared to healthy controls before (I) and after (II) treatment with sodium oxybate (voxelwise $p \leq 0.05$, corrected). Panel (III) shows significantly decreased number of hyperactive brain voxels after the treatment compared to the before treatment baseline in patients ($p = 0.017$).

Collectively, our preliminary data indicate that sodium oxybate is effective in SD patients and especially in those who present with a VT component. Furthermore, our data suggest that the effects of sodium oxybate treatment are exerted through the modulation of overly increased brain activation.

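### Aim 2's 80% power is not established for the analysis in 2.3.1: the cited 49% is a pilot fall in active-voxel count, while the plan names no primary measure and its group model has no pre/post term.

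*Combined protocol and SAP*

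**What the plan says.** The power claim is in 2.3.1, Study population and Sample size (Specific Aim #2): "Power analysis determined a sample size of 22 patients in each group to have 80% power at 0.025". The comparison it is meant to cover is the change in activation from pre-treatment to post-treatment. Its support is the sentence just before: "we found an average of 49% reduction of overly increased brain activation after treatment with sodium oxybate". No standard deviation, test or sidedness is given. The plan recruits 25 per group. Section 2.3.2 says its power is the same as in 2.3.1 and gives no calculation of its own.

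The 49% comes from 2.2.2 Preliminary Data, II. That section describes a two-tailed paired t-test "using the measure of the total number of significantly active brain voxels before and after treatment in patients", with p = 0.017. The pilot looked at "effects of sodium oxybate on brain activation abnormalities in 3 SD and SD/VT patients", which can mean 3 patients in all or 3 per group.

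The 2.3.1 Data analysis paragraph then sets the group model: "For group analysis, a two-way ANOVA will be conducted with subject as a random factor and task as fixed factor". It adds conjunction maps of the two sessions, correlations with the acoustic data, and PPI and DCM. The paragraph before it says in general terms that each patient's post-treatment scans will be compared with the pre-treatment scans. Nothing is labelled primary.

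**The concern.** A power statement is useful only if the reader can tell which test of which variable it describes. Here the supporting effect is a count of voxels above a threshold. None of the listed analyses tests that count, and the group model as written has no term for the change from before to after treatment.

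The plan itself treats the quantities as different. Section 1.3.1 distinguishes the extent of activation from its intensity. Section 1.3.4 measures brain activation as percent BOLD signal change, and the fMRI sample size in 1.3.1 uses percent signal change too. Only the Aim 2 sample size rests on a voxel count, under the same general label of brain activation.

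Two things are at stake. The 80% may not describe the test that will be run, in 2.3.1 or in 2.3.2. And voxel count, signal size, connectivity and acoustic measures can disagree, with no rule for which one answers Aim 2. The working hypothesis, greater modulation in SD/VT than in SD, has neither a model term nor a power statement.

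**Working it through.** **Inputs.** From 2.3.1: 22 per group, 80% power, 0.025, a 49% reduction, no SD. From 2.2.2: voxel count, two-tailed paired t-test, p = 0.017, pilot n of 3 or 6. From 1.3.1: percent signal change 0.63 ± 0.16 versus 0.39 ± 0.23, 15 per group.

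**Method check on Aim 1.** Pooled SD = √((0.16² + 0.23²)/2) = 0.198; d = 0.24/0.198 = 1.21. Exact noncentral-t power for a two-sided two-sample test at 0.025 is 79% with 14 per group and 82% with 15. The plan's 15 is reproduced.

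**Attempt to reproduce 22.** The SD of the change is missing, so the standardised paired effect is recovered from the pilot p-value as dz = t/√n.

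| Pilot n | t for two-tailed p = 0.017 | dz | Smallest n for 80% power, two-sided paired test at 0.025 |
|---|---|---|---|
| 3 | 7.57 | 7.57/√3 = 4.37 | 4 (76% at 3, 99% at 4) |
| 6 | 3.52 | 3.52/√6 = 1.44 | 8 (77% at 7, 85% at 8) |

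Across one- and two-sided tests, alpha of 0.0125, 0.025 and 0.05, and paired or two-sample formulas, the required n runs from 2 to 13. It is never 22. Reading 0.49 as a standardised effect gives 43 (paired, two-sided 0.025). The nearest construction takes 49% of the Aim 1 gap, 0.49 × 0.24 = 0.118, with 0.16 as the SD of the change. That gives 21, but it uses signal size instead of voxel count, and the plan does not state it.

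**What 22 implies.** Solving for 80% power at n = 22 (paired, two-sided 0.025) gives dz = 0.70. For a 49-point fall the SD of the change would be 49/0.70 = 70 points. The document gives neither figure.

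**How far power depends on the missing SD** (SDs assumed; voxel-count change as the outcome, 49-point fall, n = 22, two-sided paired test at 0.025):

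| SD of change (points) | dz | Power |
|---|---|---|
| 34 | 1.44 | >99% |
| 49 | 1.00 | 98% |
| 60 | 0.82 | 91% |
| 70 | 0.70 | 80% |
| 80 | 0.61 | 68% |
| 100 | 0.49 | 47% |

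None of this carries over to percent signal change, for which Aim 2 gives no pre/post mean or SD.

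**The analysis text beside the power text.** The power sentence refers to a before/after change. The ANOVA has subject (random) and task (fixed). A test of that change needs a session term or a paired contrast, and the SD/VT versus SD hypothesis needs group-by-session; the model has neither. The conjunction step maps common and distinct regions in the two sessions but does not estimate the change.

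**The between-group hypothesis.** With 22 per group, a two-sided two-sample test at 0.025 has 80% power for a difference in change of about 0.96 SD. The plan states no power for this contrast.

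**The case against.** Several points on the other side are fair.

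- A before/after comparison is planned in words, and the power sentence refers to it. This stands: what is missing is the variable, the test and the model term. A reader might infer that no pre/post comparison is planned; the text of 2.3.1 does not support that.
- The sample-size paragraph speaks of brain activation and does not mention voxels. That the calculation used voxel counts is inferred from the matching 49%. If another measure was used, the plan does not disclose it.
- Section 1.3.1 says that activation extent will be assessed, and 2.3.1 refers back to 1.3.1. But that reference attaches to the individual-level regression, and 2.3.1 then sets its own group model. The extent test belongs to Aim 1's task-and-group ANOVA.
- This is a mechanistic imaging study, and ranking the network analyses as secondary is partly a matter of preference. That is so, but the plan still makes a specific 80% power claim.

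Stronger readings are tempting. One is that extra scan noise after a sedating drug produced the pilot's 49%. The document gives no noise figures, the effect of noise on a voxel count depends on how close voxels lie to the threshold, and the plan includes motion regressors, sparse sampling and head immobilisation. Another is that Aim 2 could be declared positive on a voxel count alone; under 2.3.1 as written that would be an unplanned analysis. A third is that all the listed analyses are interchangeable routes to success with an inflated error rate. PPI and DCM are introduced as additional, so the text does not make them so.

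**Conclusion.** The concern holds in this form: the 80% power is not established for the analysis described in 2.3.1, and 2.3.2 inherits the gap. The cited 49% is a voxel-count result from a pilot of 3 or 6 patients. No listed analysis tests that measure, no measure is primary, and the stated ANOVA contains neither the pre/post change nor the group difference in it.

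The figure of 22 cannot be traced: the pilot p-value leads to 4 or 8 patients, and 22 needs a standardised change of about 0.70 that is not stated. This rests on recovering the effect from a rounded p-value, on a two-sided paired test at 0.025, and on the 49% being the same result in both sections. A reader might infer that 22 is wrong or too small. The document does not show that, because the SD of the change and the sidedness are missing, and the pilot taken at face value would need fewer patients.

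The data would remain usable. This should be corrected before analysis, as a matter of specification and honest reporting of power.

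**What to change.** In 2.3.1:

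1. Add session (pre/post) to the group model. Name as primary the paired pre-to-post change in percent BOLD signal change, in one named task, within each group at corrected p ≤ 0.025.
2. State the SD/VT versus SD difference in that change (group-by-session) as the test of the working hypothesis, with no power claimed for it.
3. Report the active-voxel count as descriptive. Label PPI, DCM and the voice correlations secondary.
4. Restate the power sentences in 2.3.1 and 2.3.2: the 49% cited is a voxel-count result from a small pilot, and power for the planned contrast has not been established.

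This needs no new patients, scans or data. It is more than a change of wording, because the group model has to be respecified. The cost is a less favourable power statement and a secondary label for the network results.
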